7.2. STUDY EVALUATIONS METHODS

7.2.1. Nasal Obstruction Symptom Evaluation (NOSE) Scale

The Nasal Obstruction Symptom Evaluation (NOSE) Scale¹⁸ is a Patient-Reported Outcome (PRO) instrument that will be administered to capture subject perception of the degree of nasal airway patency.

The NOSE scale will be completed at the Screening, Baseline, 1 Month, 3 Month, 6 Month, 12 Month, 18 Month and 24 Month visits. In the event that the Screening & Baseline Visits occur on the same day, only one NOSE score is required. The NOSE scale may additionally be completed at the Treatment Visit if more than one (1) month from Screening Visit.

The NOSE scale is a validated instrument, which was developed by the American Academy of Otolaryngology—Head and Neck Surgery (AAO-HNS), and has been used in several clinical trials. The scale is brief, easy to complete, and is an important tool for pre- and post-intervention evaluation of symptoms in subjects with nasal obstruction. NOSE Scale allows subjects to quantify their symptoms based on the severity of obstruction.

Subjects will be asked: "Since your last follow up visit, how much of a problem were the following conditions for you?" Specifically, subjects will be asked to rate their perceptions on the Likert scale with respect to the following characteristics:

- Nasal congestion or stuffiness
- Nasal blockage or obstruction
- Trouble breathing through my nose
- Trouble sleeping
- Unable to get enough air through my nose during exercise or exertion

Subjects will rate their responses using a Likert scale with response options 0, 1, 2, 3 or 4, as follows:

- (0) Not a Problem
- (1) Very Mild Problem
- (2) Moderate problem
- (3) Fairly Bad Problem
- (4) Severe problem

The responses are rated along the continuum, with a rating of “0 – not a problem” indicating no problem breathing, with a completely free flow of air through the nasal airway; “1 – very mild problem”, with only slight obstruction in airflow; “2 – moderate problem”, with mouth breathing considered easier; “3 – fairly bad problem,” with considerable obstruction to airflow; and a rating of “4 – severe problem,” with complete blockage and obstruction of the nasal passageway, where the subject cannot breathe through the nose and can only mouth breathe. A copy of the Nasal Obstruction Symptom Evaluation Scale questionnaire is attached (See Appendix V).

7.2.2. NAO Breathing Assessment

A subject's perception of breathing cannot be quantitatively measured, but exists on a continuum from the subject perspective. A Visual Analog Scale (VAS) is a PRO instrument that will be used to capture subjects' perception of their ability to breathe through the nose, allowing subjects to indicate the degree of breathing difficulty (or ease) they are currently experiencing. The NAO Breathing Assessment will be completed at the Baseline, 1 Month, 3 Month, 6 Month, 12 Month, 18 Month and 24 Month visits for non-training subjects.

Operationally a VAS is a horizontal line, 100mm in length, anchored by word descriptors at each end, as illustrated in Figure 3.

The subject will either mark on the line the point that they feel represents their perception of their current state or will communicate the information to the Study Coordinator verbally, who will, in turn, mark the form as indicated by the subject. The VAS score is determined by measuring in millimeters from the left end of the line to the point marked by the subject.

Figure 3: Visual Analog Scale. Left side represents 0mm and right side represents 100mm.

7.2.3. Epworth Sleepiness Scale (ESS)

The Epworth Sleepiness Scale (ESS) is a widely-used PRO in the field of sleep medicine as a subjective measure of a patient's sleepiness. Non-training case subjects will complete the ESS Assessment at the Baseline, 1 Month, 3 Month, 6 Month, 12 Month, 18 Month and 24 Month visits.

The test is a list of eight situations that evaluate a subject's tendency to become sleepy on a scale of 0 (no chance of dozing), to 3 (high chance of dozing). The scale estimates whether the subject is experiencing excessive sleepiness that may possibly require medical attention.

Subjects will be asked: "How sleepy are you? How likely are you to doze off or fall asleep in the following situations? You should rate your chances of dozing off, not just feeling tired. Even if you have not done some of these things recently try to determine how they would have affected you. For each situation, decide whether or not you would have:

- No chance of dozing =0
- Slight chance of dozing =1
- Moderate chance of dozing =2
- High chance of dozing =3

Using the above scale, subjects will write down the corresponding choice to the following situations:

- Sitting and reading
- Watching TV
- Sitting inactive in a public place (e.g. a theater or a meeting)
- As a passenger in a car for an hour without a break
- Lying down to rest in the afternoon when circumstances permit
- Sitting and talking to someone
- Sitting quietly after lunch without alcohol
- In a car, while stopped for a few minutes in traffic

The responses to the above situations is totaled for a final score.

A copy of the ESS questionnaire is provided in **Appendix VI**. In order to avoid bias, the version of the ESS provided as a PRO to the subjects will not include the "Analyze Your Score" section of the questionnaire.

7.2.4. Baseline Health Economics Questionnaire

The Baseline Health Economics Questionnaire is a non-validated, Spirox-developed PRO used to document the frequency and type of doctor visits related to the Nasal Airway Obstruction condition over the one year prior to study enrollment. Non-training case subjects will complete the questionnaire at the Baseline Visit.

7.2.5. Post Procedure Health Economics Questionnaire

The Post Procedure Health Economics Questionnaire is a non-validated, Spirox-developed PRO completed at follow-up visits. The Post-Procedure Questionnaire differs from the Baseline version with regards to the timeframes that are referenced. The post-procedure health economics survey will document frequency and type of doctor visits related to the Nasal Airway Obstruction condition since the index procedure, excluding study visits. Non-training case subjects will complete the Questionnaire at the 1 Month, 3 Month, 6 Month and 12 Month visits.

7.2.6. Demographics & Nasal Medical History

Demographic information, such as age, gender, ethnicity, race and date of onset of nasal obstruction will be ascertained for all subjects at the Baseline Visit.

The past five years of relevant nasal medical history will include a complete review of nasal systems and evaluation of symptoms, including an assessment of nasal airway obstruction signs and symptoms. A history of prior nasal trauma or nasal surgery will be noted, as well as other medical conditions related to head and neck and respiratory conditions. Questions will be asked about the medications used by the subjects,

including the types and doses of medications that are used to control nasal obstruction symptoms and the performance of those medications in controlling their symptoms (i.e., OTC medications, nasal sprays, decongestants, nasal airway devices, etc.).

7.2.7. Baseline Nasal Exam

A Baseline Nasal Exam will be conducted for all subjects at the Baseline Visit. The exam will include collection of nasal anatomy parameters such as nose length, nose height, nose width and skin thickness.

In addition, each side of the nose will be examined with an endoscope to assess each subject's degree of inferior turbinate hypertrophy and septal deviation (superior and inferior). Each of these will be graded as Normal, Mild, Moderate, or Severe.

7.2.8. Post Procedure Nasal Exam

An internal and external nasal visual physical exam will be conducted at each follow-up visit to document any changes in nasal appearance. A nasal exam will be conducted for training case-subjects at the 1 Month follow-up visit, and for non-training case subjects at the 1, 3, 6 and 12 Month follow-up visits.

Any observation during the exam regarding the Implant, such as a bent or fractured Implant, or any evidence that the Implant has moved or migrated from its intended target location (without resulting in retrieval) shall be recorded.

Additionally, non-training case subjects, at all Follow-Up Visits, will have each side of the nose examined with an endoscope to re-assess each subject's remaining degree of inferior turbinate hypertrophy and septal deviation (superior and inferior). Each of these will be graded as Normal, Mild, Moderate, or Severe.

7.2.9. Modified Cottle Maneuver

In order to confirm that the subject has dynamic lateral wall insufficiency (LWI), the Modified Cottle Maneuver should be performed. The assessment will be done at the Screening and Baseline visits.

To test for LWI, the curette, cerumen loop, or similar instrument should be inserted into the nasal cavity and used to gently support the lateral nasal sidewall while the patient is asked to breathe in. The Subject will be asked to verbally report their relative improvement per side using the scale below (See **Figure 4**).

Figure 4: Verbally reported improvement in breathing with supported lateral wall.

7.2.10. Lateral Wall Motion Video

Videos will be captured at the Baseline, 1, 3, 6, and 12 Month follow-up Visits for all non-training case Subjects. Videos will be transferred to Spirox and will be blinded prior to transfer to independent reviewer. The independent reviewer will make assessment of endoscopic lateral wall insufficiency score (1, 2 or 3). Some sites may also capture additional endoscopic videos in conjunction with a mask designed to facilitate the collection of the subject's nasal airflow rate. Use of the nasal airflow rate mask will be limited to approximately three sites and subject participation is optional.

Spirox will utilize the HIPPA compliant file transfer protocol website (BrickFTP.com) BrickFTP site for the transfer of all images and videos from the site to Spirox for processing and analysis. Each site will only have access to upload and view images in their assigned folder(s) and will not have access to other site's folders on the BrickFTP.

See [Appendix VII](#) "Lateral Wall Motion Capture Instructions".

Lateral Wall Motion Videos will not be captured for Training Case Subjects.

7.2.11. Photography - Cosmetic

At select sites, photographs will be captured at the Baseline, 3 and 6 Month follow-up Visits for non-training case subjects to evaluate potential cosmetic changes.

Review of the nasal appearance changes attributed to the overall procedure as well as those attributed to the Latera Implant will be assessed by an independent physician reviewer.

Photographs will be taken to record baseline nose appearance to evaluate aesthetic changes. Six (6) photographs will be taken: five (5) static photographic views (straight, left side, right side, chin-up and chin-down) will be taken and two (2) at a full inhale photographic views (chin-up view and top-down).

Images will be blinded (e.g. black boxes placed over the eyes) by the sponsor prior to being sent to the independent reviewer. Images will be transferred using BrickFTP site.

See [Appendix VIII](#) "Cosmetic Photo Capture Instructions".

Cosmetic Photography will not be captured for Training Case Subjects.

7.2.12. Photography – 3D

At select sites, 3D Images will be captured at the Baseline, 3, 6 and 12 Month follow-up Visits for non-training case Subjects.

3D Image capture will be used to evaluate baseline and post-procedure changes regarding the depth and volume of nasal collapse at approximately two sites. 3-D photography review will be limited to approximately 3 sites, and subject participation is optional. Site selection for participation will be based on adequate facility space and staff to support this additional component. Subject participation in 3D photography is optional.

The Canfield Vectra H1 handheld imaging system allows for the capture and analysis of 3D images. The system is comprised of the Vectra H1 camera, Mirror® software and VECTRA Analysis Module. The Vectra H1 camera has an integrated flash to simultaneous capture photographs from dual-angles to build 3-D images. Photographs are either captured to the camera's SD card or tethered to a workstation. Photographs are captured and managed using Canfield Mirror® software and is analyzed with Canfield VECTRA Analysis Module. Images will be saved with the camera-generated sequence number (e.g. photo "38"), and then transferred for analysis using the subject ID and study visit for identification.

Images will be transferred using BrickFTP site.

See [Appendix IX](#) "3D Camera Image Capture & Transfer Instructions".

3D Images will not be captured for Training Case Subjects.

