10.6. MEASURES TO MINIMIZE BIAS

This is a single arm, open label study. Randomization and blinding are not used.

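### The plan does not provide for masking image assessors to time point, which leaves the exploratory video, 3D and cosmetic before/after results open to expectation bias

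*Combined protocol and SAP*

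**What the plan says.** Section 4.2.3 lists three image-based endpoints: a lateral wall insufficiency score per side, 3D wall motion per side, and cosmetic change judged by independent photo review. The section describes all its endpoints as exploratory and informational.

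- **Video (7.2.10):** recorded at baseline and at 1, 3, 6 and 12 months. "Videos will be transferred to Spirox and will be blinded prior to transfer to independent reviewer". The reader gives a score of 1, 2 or 3. The same section sets up the file site "for the transfer of all images and videos from the site to Spirox for processing and analysis".
- **Cosmetic photographs (7.2.11):** taken at baseline, 3 and 6 months at select sites. "Images will be blinded (e.g. black boxes placed over the eyes) by the sponsor prior to being sent to the independent reviewer". The physician reader's task is described as "Review of the nasal appearance changes attributed to the overall procedure as well as those attributed to the Latera Implant".
- **3D images (7.2.12):** taken at baseline, 3, 6 and 12 months at select sites, with optional participation. Files are saved under the camera's sequence number and "then transferred for analysis using the subject ID and study visit for identification". The captured material "is analyzed with Canfield VECTRA Analysis Module". The section mentions no blinding and no independent reader.

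Section 10.6, on measures against bias, describes a single-arm open-label study and says "Randomization and blinding are not used".

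**The concern.** Section 10.4.1 makes each subject their own control. For an image read, the mask that protects the comparison is therefore the mask on time point. Hiding who the subject is does not hide whether the picture was taken before or after the implant.

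An assessor who knows the visit may, without intending to, grade a follow-up video as more stable than the same video would be graded blind, or judge a follow-up photograph as unchanged. Both tendencies favour the device. Video and cosmetic review are the two assessments that the plan gives to an independent reader, and in an open-label study that independence is worth less if the reader can see the visit. Appendix II says the data may support regulatory applications and publications. A result reported there as an independent blinded read would be understood as masked to time point.

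**Working it through.** No figure in the plan depends on the image reads, so the check compares the text for the three assessments.

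| | Video (7.2.10) | Cosmetic (7.2.11) | 3D (7.2.12) |
|---|---|---|---|
| Blinding stated? | Yes | Yes | No |
| Measure named | None | Eye boxes, as an example | None |
| Visit label | Not mentioned | Not mentioned | Used to identify the file at transfer for analysis |
| Reading order | Not mentioned | Not mentioned | Not mentioned |
| Assessor | Independent reader | Independent physician | Not named; software analysis |

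1. **3D.** This is the only assessment for which the text puts the visit on the file. No later step removes it, so by the text the analysis is visit-labelled.
2. **Cosmetic.** The one illustrated measure is de-identification. Section 7.2.15 gives the same illustration for discretionary images. Wherever the protocol explains what blinding an image means, the explanation concerns identity.
3. **Video.** Eye boxes would mean little on an endoscopic recording, so blinding must mean something else here. The text does not say what. Masking of visit can be neither confirmed nor excluded.
4. **Path to the results.** Section 10.4.11 cross-tabulates the 3-level score over visits and reports the proportion improved. Let u be the share of sides that a masked reader would score as unchanged, and d the share of those that move one grade better because the visit is known. The reported proportion improved then rises by d × u with no true effect. The documents give neither d nor u, so the product cannot be evaluated from them.
5. **Path to the primary analysis.** There is none. The only formal hypothesis (10.2) concerns NOSE responders at 6 months, and the sample size of 150 with 6-month follow-up (10.5) uses no image input.

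**The case against.** The strongest reply is that silence is not disclosure. The eye boxes are introduced as an example, so other measures are not ruled out. The videos are expressly promised blinding. The 3D sentence describes a transfer label, which some intake step needs so that files can be linked to subjects, and 7.2.12 makes no blinding promise that could fail. Software measurement may also leave less room for judgement than a grading, though the text does not say how much operator input it needs. The instructions in Appendices VII to IX are not in the available text, so any labelling rules there cannot be checked.

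These points stand, and they limit the claim to what the plan fails to specify. They do not supply the missing statement: blinding whose object is undefined can be neither implemented consistently nor verified.

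A reader might infer several stronger conclusions that the documents do not support:

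- **That assessors will receive dated images in time order.** No section says this.
- **That 10.6 withdraws the image blinding promised in 7.2.10 and 7.2.11.** Its natural meaning is that treatment is not blinded.
- **That these are the only outcomes not reported by subjects.** Investigators judge adverse event severity and relatedness (8.2) and grade the turbinates and septum by endoscope (7.2.8).
- **That the cosmetic reader cannot separate implant from procedure.** This is a different question and the text does not settle it. Section 7.4 describes turbinate tissue removed from inside an intact lining, and 10.3 defines a stand-alone population.

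**Conclusion.** The gap is real but limited. The plan does not provide for masking assessors to visit in any of the three image assessments. For 3D the visit label is explicit, for cosmetic photographs only de-identification is illustrated, and for video the scope of blinding is undefined. Expectation bias in favour of the device is therefore possible in the exploratory lateral wall, 3D and cosmetic results.

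Its size cannot be derived from the documents. One could assume drift on 5–15% of unchanged sides and 40–60% of sides unchanged, which gives 0.05 × 0.40 = 2 to 0.15 × 0.60 = 9 percentage points. Both inputs are assumptions with no source in the plan, and the score they concern is the one for which blinding is promised. The range should not be read as an estimate.

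The primary efficacy endpoint, its test, power and sample size are untouched, and 10.4.9 already asks for caution with everything else. The point is a cheap improvement of low severity. It assumes that the unseen appendices do not already contain a rule for masking visit; if they do, a cross-reference in 7.2.10–7.2.12 would be enough.

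**What to change.** In 7.2.10–7.2.12, state the following:

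- Before any assessment, the sponsor replaces subject ID, date and visit with a random code. The intake label is kept only in the linking key.
- Videos and 3D files are scored singly, in random order across visits. For 3D, the role that performs the analysis is named.
- Cosmetic photographs are shown as pairs in random order without visit labels. If the attribution question in 7.2.11 needs the order to be known, it is answered after the masked score is locked.
- The key is released only after scores are locked.

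A sentence in 10.6 can separate open-label treatment from masked image reading. The SAP, which 10.1 says is still to be finalised before database lock, can repeat the rule.

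The cost is a small amount of file handling. The sponsor already receives all files and blinds videos and photographs before the independent read, so no new images, visits or readers are needed. Two limits remain. Some views may still reveal the time point. The cosmetic reader will also know that one photograph of each pair was taken after the procedure, so random order removes bias in the direction of change but not a general leniency towards scoring no change.

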7.2.13. Assessment of Turbinate Hypertrophy Contribution to NAO

After completion of all other assessments at the Baseline Visit, non-training case subjects will be asked to assess their ability to breath after a decongestant (e.g. Afrin) has been administered. Administration of a decongestant is frequently used to diagnose significance of inferior turbinate contribution to NAO. After decongestant administration, subjects will be asked to rate their degree of nasal airway obstruction using the VAS scale (See Section 7.2.2).

7.2.14. Subject Satisfaction Questionnaire

The subject satisfaction questionnaire is a non-validated, Spirox-developed PRO form that will contain the questions related to subject satisfaction with the procedure and their nose appearance. Non-training Case Subjects will complete the Questionnaire at the 1 Month, 3 Month, 6 Month and 12 Month visits.

7.2.15. Discretionary Imaging

In addition to the protocol specific imaging outlined above, the Investigator may wish to share, or Spirox may request, additional images (digital photos) or videos of subject for the purposes of, but not limited to, consultation (e.g. placement of device ahead of procedure, etc.), documentation of changes (e.g. cosmetic change, lateral wall motion, etc.) or adverse event reporting (e.g. image of hematoma). Images may include endoscopic nasal video, digital video or photography. Images or videos may be taken at any time point during the study.

Digital images will be blinded (e.g. black boxes placed over the eyes). Images may be used for educational and/or research purposes only. Images or videos will be transferred to Spirox using BrickFTP.

7.2.16. Latera™ Patient Experience and Testimonials

Subjects that have enrolled in the study may also be invited to participate in "Latera™ Patient Experience and Testimonials". This invitation may occur at time of Screening or at any time point through study exit.

Spirox may choose to capture Latera™ patient experience and/or testimonials through film, videotape, photographs and/or quotes. Spirox may choose to capture the testimonials prior to, during and after the LATERA procedure is performed, at varying intervals (i.e., day of procedure, 1 week post-procedure, 1 month post-procedure, etc.). Spirox and the investigational sites may use these photographs, videos, personal images and quotes in whatever medium deemed appropriate by Spirox for any of the following purposes: (i) educational and research purposes, (ii) medical or audiological consultations, (iii) publication in professional journals, (iv) collateral and promotional materials, (v) web-based marketing materials including website content, (vi) public and media relations, or any other advertising methodology.

For these subjects, written consent in the form of an IRB approved addendum to the study ICF will be required. Participation is optional and will not impact their participation in the study. Consent to participate does not guarantee that they will be selected as a participant. No additional reimbursement beyond what is outlined in Section 5.3 will be provided.

